3. MATERIAL AND METHODS

3.1. TYPE OF STUDY

This is a randomized prospective study comparing two groups of patients with distal radius fracture during a year

A → Local Anaesthesia (WA) LANT + NO ISCHEMIA +/- sedation.

B → Locoregional anaesthesia proximal block + ISCHEMIA +/- sedation.

3.2. INCLUSION AND EXCLUSION CRITERIA

Inclusion criteria will be those patients ≥18 years of age who agree to participate.

Patients with any of the following conditions will be excluded from the study:

1. Do not sign informed consent.
2. They have associated fractures in which additional osteosynthesis is required: scaphoid fracture, ulnar fracture, bifocal radius fractures, etc.
3. Open fractures.
4. Polytrauma
5. Non-synthesized flying fractures with a single plate or other type of plate.
6. Patients in whom a different surgical technique than the one mentioned above has been required.
7. Contraindications to the use of ischemia (14)

- a. Peripheral vascular disease.
- b. Seriously injured or traumatized limb.
- c. Peripheral neuropathy or CNS disease
- d. Severe infection in the limb.
- e. Thromboembolic disease in the extremity.
- f. Poor skin condition of the limb.
- g. Arteriovenous fistula.
- h. Sickle cell hemoglobinopathy.

8. Contraindications for proximal blocking: (15)

- a. Existence of previous trauma or anatomical distortion of the area that prevents the abduction of the arm.

- b. Active presence of infection at the puncture site.
- c. Previous axillary lymphadenopathy.
- d. Previous history of local anaesthetic allergy.
- e. Severe coagulopathy.
- f. Severe pre-existing neurological diseases in the upper extremity.

9. Contraindications for WALANT anaesthetic technique

- a. Documented hypersensitivity to lidocaine.
- b. Compromised peripheral circulation.
- c. Patients with previous vascular pathology, a history of vasculitis, Buerger's disease, and scleroderma.
- d. Patients with infection of the area surrounding the injection.

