The most commonly used drug for local anaesthesia is lidocaine, as it is the prototype short-acting anaesthetic and its physicochemical properties (solubility, relative potency, onset of action and duration) are those indicated to perform this type of procedure. The injection of lidocaine may or may not be associated with adrenaline, which produces vasoconstriction, decreasing local bleeding in the area, and at the same time prolongs the action of lidocaine. This combination of drugs can extend the duration of anaesthesia up to 3 hours. That is why in the WALANT technique these two drugs are administered together. Lidocaine is administered with a 1% (10mg / ml) solution, and if larger volumes or lower doses of anaesthesia are required, 0.5 of the solution may be used to avoid the maximum toxic doses, which in the combination of adrenaline + lidocaine, the maximum toxic dose is 7mg / kg with a maximum total dose of 500mg (50ml of 1% Lidocaine or 10cc of 5% Lidocaine). Concentrations above 1% lidocaine are not used, as they have not been shown to improve induction or duration of anaesthesia and may increase the risk of toxicity. In order to counteract the acidic pH of lidocaine, it is buffered with 8.4% (1M) sodium bicarbonate in a 10: 1 ratio, thus reducing pain during administration. This type of anaesthesia is performed according to the Lalonde's technique and is administered according to the Ahmad technique. (10) (22) (23) (24)

Our hypothesis is that the application of this anaesthetic technique, combined or not with sedation, causes less swelling and pain in the immediate postoperative period, without compromising patient satisfaction, altering short-term results or increasing the number of complications and without increasing the technical difficulty of the procedure to the surgeon.

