2.2. SECONDARY OUTCOMES

1. Evolution of the surgical wound (active bleeding and dressing condition at 24 hours and 10-15 days after surgery)
2. Postoperative mobility
 - a. Thumb mobility and opposition (Kapandji scale)
 - b. Finger mobility (capability of the patient to arrive at proximal and distal palm crease)
 - c. Wrist mobility (flexion, extension, pronation, supination, ulnar deviation, radial deviation)
3. Surgeon's technical difficulty.
 - a. Scale 1-5 (1 easy- 5 difficult)
 - b. Intraoperative stress /yes/no) and reason
4. Insufficient anaesthesia
 - a. Need of change to General Anaesthesia
 - b. Need of adding more anaesthesia
 - i. Type of anaesthesia used (sedation, local anaesthesia reinforcement, etc.)

- ii. Reason for change
- 5. Postoperative complications (total number and description)

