3.3. VARIABLES

Independent variables:

These variables will be collected during the surgery and in the subsequent from patient anamnesis, clinic history and filling the Collection Data Guide Form:

- Age (years)
- Sex (male / female)
- Dominant hand (left / right / both)
- Injured hand (left / right / two)
- Fracture classification according to American Orthopaedic (AO) (16), (17)
- Number of days from injury to surgery (days)
- Preoperative pain (VAS scale (18))
- Preoperative swelling injured hand and healthy hand. The perimeter of the wrist will be measured at the height of the proximal palmar fold in cm.

Dependent variables:

These variables are the ones we want to study and will be collected during the surgery and afterwards from patient anamnesis, clinic history and filling the Collection Data Guide Form:

- Duration of admission (hours).
- Duration of surgery (minutes).
- Duration of ischemia in group B (minutes).

- Preoperative and postoperative pain (VAS scale): Pain at baseline, 24 hours post-intervention, at the visit of the first treatment 10-15 days post-intervention and pain 1 month after the intervention.
- Intraoperative pain (VAS scale): Assessable only if it has not required sedation.
- Time (minutes) of anaesthesia administration
- Time (minutes) from the end of administration to the beginning of IQ
- Need for anaesthetic reinforcement:
 - Sedations (yes/no) and reason
 - In the case of WALANT: Taking into account the reference technique used (10), if any extra doses are needed and location within the wrist
- Postoperative analgesia during admission and discharge (drugs used, dose and frequency of use)
- Postoperative swelling injured hand and healthy hand (cm).
- Stained dressing and the presence of active bleeding due to the wound within 24 hours and during the first outpatient clinic 10 or 15 days after surgery.
- Patient satisfaction during the first outpatient clinic 10 or 15 days after surgery. → Assess satisfaction (1-5) / Would you repeat the anaesthesia type? / Would you recommend the technique?
- Description of the complications of anaesthesia.
- Description of postoperative complications.
- Mobility 24 hours post-intervention, first aid and one month later. (The mobility of the fingers, intrinsic and extrinsic muscles, Kapandji exercises 1-10 and wrist mobility will be assessed by measuring flexion-extension and prone-supination with a goniometer).
- Surgeon's experience

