3.4. DATA COLLECTION AND INSTRUMENTS

A sample of patients with a distal radius fracture operated in our Hospital will be obtained. Those who meet the inclusion criteria will be asked to participate and will be told what the study is about. Those who accept must sign the specific informed consent of this study.

Prior to surgery, an external observer will collect the personal data of the patients, assign them a code (P1, P2, P3...) and perform the anamnesis following the Data Collection Guide Form

Patients' recruitment will be done during a year, from December 2020 to December 2021. They will be separated into two groups. The external observer will do this process with 10-block randomization using Study Randomizer (2017), a web based randomization service (19)

The first (Group A) in which WALANT technique will be performed and the second (Group B) in which locoregional anaesthesia (either axillary or supraclavicular block) with axillary ischemia will be applied. Because it is considered a long-term intervention, all patients will be offered the option of sedation or not, and this variable may change depending on the criteria of anaesthesia or the patient himself in order to facilitate their well-being. All patients participating in the study will receive the same antibiotic prophylaxis following our protocol (Cefazolin 1g iv in <80Kg or 2g 80-160Kg and in patients with normal renal function, to pass in 5 minutes. In those with FG The dose should be adjusted, and a second dose of 2g iv should be given if the surgery lasts 3 hours or more. In patients with penicillin allergy, Teicoplanin 600mg iv will be administered in 10 minutes, without repeating the dose. in no case) (20)

Group A (WALANT Anaesthesia +/- sedation + NO ischemia)

In WALANT technique, the doses are followed according to Lalonde's (21). 1% lidocaine with 1: 100,000 adrenaline is generally used to counteract the acidic pH of lidocaine, which is buffered with 8.4% (1M) sodium bicarbonate in a 10: 1 ratio to decrease pain during administration. If more volume is required, Lidocaine is diluted to 0.5% so as not to exceed the maximum toxic dose of 7mg / kg with a maximum total dose of 500mg (50ml of 1% Lidocaine or 10cc of 5% Lidocaine) (22)

In this case, the preparation will be made by the nurse with 100cc of SF, from which 15cc will be extracted and 10cc of 5% Lidocaine + 1cc Adrenaline + 4cc of 1M Bicarbonate will be added.

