Anaesthesia will be administered in the operating room, monitoring the patient's HR, BP, and SatO2. It will take 20-30 minutes before starting the surgery, as the peak of vasoconstrictor action of the adrenaline is reached after this time.

The technique according to Ahmad (10) is to infiltrate 40ml of local anaesthetic preparation, distributing 10ml to the subcutaneous tissue along the approach, from proximal to distal. Subsequently, 30ml is administered in deeper planes divided into

3 points, from proximal to distal, distributed in 4ml around the flying periosteum, 2ml radially and 4ml in the dorsal periosteum, through a lateral entrance, introducing the 'needle from the radial side avoiding puncturing through the radial artery. An additional 10ml will be added for the intra-articular region, using conventional 3-4 and 6R arthroscopy radiocarpal approaches. In some cases it may be increased if the surgeon considers that it requires more volume, as long as we do not exceed the toxic doses (23).

In patients with a history of cardiac pathology, it is possible to assess the possible dissolution of adrenaline at 1: 400000, this group will include those patients with ischemic heart disease and / or severe hypertension (irregular hypertension with the use of 3 different antihypertensive drugs).

Group B (Locoregional anaesthesia proximal block +/- sedation + ischemia)

The anaesthesiologist in charge of the operating room will perform the locoregional block. The same ischemia sleeve (size, brand, manufacturer and country of origin) will be used on all patients and the same ischemia pressure (250mmHg) will be applied.

In all of them, intraoperative monitoring will be performed, which will be the same in both groups, the FC, FR, TA, ECG, SatO2 and duration of the intervention must be recorded.

The surgical procedure will be the same for all patients. If the surgeon considers it necessary, arthroscopic assistance will be used with conventional dorsal radiocarpal portals (2-4R and 6R). Surgeons from the surgeons of our Upper Extremity Unit will perform all operations.

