3.6 STATISTICAL PLAN

Quantitative values will be described as mean and standard deviation in case of normal distribution, or with median and interquartile range otherwise. Qualitative variables will be described with absolute and relative frequencies. The Student's t test for normal quantitative variables and the non-parametric Mann-Whitney U test will be used to compare the two experimental groups. Pearson's chi-square test for expected frequencies above 5 and Fisher's exact test would be used to compare the distribution of qualitative variables between groups. Statistical program R [ref] will be used, applying a statistical significance level of 5%.

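### Exclusion criterion 6 can remove randomised patients because of a change of surgical technique known only at or after the operation, and no analysis rule offsets this

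*Combined protocol and SAP*

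**What the plan says.** All references are to the combined protocol and SAP.

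- **Section 3.2.** Patients meeting any listed condition are out of the study, not merely out of one analysis. Criterion 6 lists "Patients in whom a different surgical technique than the one mentioned above has been required". Criterion 5 lists "Non-synthesized flying fractures with a single plate or other type of plate", without saying whether planned or actual fixation counts.
- **Section 3.4.** An external observer codes patients and takes the history before surgery, and also performs the randomisation in blocks of 10. Only the inclusion criteria are mentioned as a check before consent. On the operation itself: "The surgical procedure will be the same for all patients. If the surgeon considers it necessary, arthroscopic assistance will be used". The procedure is not defined further.
- **Section 3.3.** No variable records the fixation used. Duration of ischemia is listed for group B only.
- **Section 3.6.** The t test or Mann-Whitney test "will be used to compare the two experimental groups". No analysis set is named, and there is no rule for patients excluded after randomisation.
- **Section 2.2.** Anaesthetic failures are kept as outcomes, including "Need of change to General Anaesthesia" and the need for added anaesthesia.

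**The concern.** Randomisation protects the comparison only while the patients analysed are those who were randomised. A patient who turns out during the operation to need another technique meets criterion 6 after the arm has been assigned. The surgeon can see whether a tourniquet is in use, so the arm could influence the decision to change technique. If such exclusions differ between arms and the patients concerned also differ in outcome, the difference in pain, swelling or satisfaction no longer estimates the effect of the allocated anaesthetic alone.

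The protocol's own text makes both conditions plausible without establishing either. Section 3.3 has the surgeon rate difficulty arising from poor visualisation of the field. Section 3.5 (Limitations of the study) says more complex fractures can be more painful, and pain is a primary outcome. Because technique changes are not a listed variable, a reader of the results could not tell from the listed data whether the exclusions were balanced.

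**Working it through.** **Step 1: order of events.** Section 3.4 does not state when randomisation takes place. The arm fixes the anaesthetic, and group A is infiltrated 20-30 minutes before surgery starts, so allocation must precede the operation. This is an inference.

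**Step 2: what criterion 6 refers to.** It is in the past tense, about a technique that proved necessary. Criterion 2, on additional osteosynthesis, is in the present tense and can be judged at screening. The contrast supports reading criterion 6 as an operative event. Its reference technique is unclear: the nearest candidate is the plate fixation in criterion 5, and section 3.4 leaves the common procedure undefined.

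**Step 3: is there an offset?** None was found. Section 3.6 has no as-allocated rule, and section 3.3 lists neither the fixation used nor tourniquet use in group A. The data collection form is not among the documents.

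**Step 4: possible size.** The plan gives no figure to reproduce. It supplies only the 5% significance level; a two-sided test is assumed. Every other input below is an assumption.

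Let p be the fraction of an arm excluded and g the mean excess (worse) score of excluded over retained patients. If R is the retained mean, the full-arm mean is (1 − p)R + p(R + g) = R + pg, so exclusion lowers the arm mean by pg. Hence

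shift in (A − B) = −(pA·gA − pB·gB).

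With g = 2 VAS points in both arms, a negative shift favours WALANT:

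| Excluded in A | Excluded in B | Shift (VAS points) |
|---|---|---|
| 10% | 10% | 0 |
| 10% | 5% | −(0.20 − 0.10) = −0.10 |
| 5% | 0% | −0.10 |
| 10% | 0% | −0.20 |
| 15% | 0% | −0.30 |
| 0% | 10% | +0.20 |

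False-positive rates come from 40,000 simulated trials per case: normal outcome, equal true means, two-sided t test at 5%, g = 1 SD.

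| Excluded A v B | 30 per arm | 50 per arm | 100 per arm |
|---|---|---|---|
| 5% v 0% | 5.4% | 5.8% | 6.4% |
| 10% v 0% | 6.6% | 7.7% | 10.5% |
| 15% v 0% | 8.3% | 11.2% | 17.3% |

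At 50 per arm, 10% v 5% gives 5.5% and 10% v 10% gives 5.0%. For 0% v 10% it is 7.3%, with most false positives favouring group B. For 10% v 0% with g = 0 it is 5.0%. Analysing all randomised patients gave 4.7% to 5.2% in every case.

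**Step 5: check by formula.** In SD units, with b the shift, SE = √(1/[n(1 − pA)] + 1/[n(1 − pB)]) and type I error = Φ(−1.96 + b/SE) + Φ(−1.96 − b/SE). For n = 50 and 10% v 0%: b = −0.10, SE = √(1/45 + 1/50) = 0.2055, |b|/SE = 0.487, so Φ(−1.473) + Φ(−2.447) ≈ 0.070 + 0.007 = 0.077, in line with the simulation. For 15% v 0% the formula gives 11.1%; at n = 100 and 15% v 0% it gives 17.4%. Halving the gap to 0.5 SD halves the bias: 10% v 0% at n = 50 then gives 5.7%.

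The two illustrations use different scales. They coincide only if the VAS standard deviation is 2, which the documents do not state.

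**The case against.** The strongest reply is that section 3.2 is an eligibility list, most of whose items can be settled before surgery. Read with criterion 5, criterion 6 may simply restrict the trial to one planned type of fixation. The text is visibly translated, so a verb tense is thin evidence. That reading is possible, but it fits the wording less well than the operative one, and nothing in the document limits the criterion to the preoperative plan. Even on that reading, the wording has to be clarified.

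Second, the link to the arm is not demonstrated. Choice of fixation may follow the fracture pattern, which randomisation balances on average, and the failures most directly tied to WALANT are retained as outcomes in section 2.2. The Introduction also hypothesises that WALANT works "without increasing the technical difficulty of the procedure to the surgeon". This stands as a limit on what can be claimed: bias is possible, not shown, and its direction is open.

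Third, the larger false-positive rates rest on one-sided exclusion and a full 1 SD gap. That is correct, and with milder or balanced exclusions the effect is small or nil.

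Fourth, the clinical record or the data form might hold the technique used, and reasons for intraoperative stress are recorded in both arms. These could reveal some cases, but they do not provide a planned count by arm.

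**Conclusion.** The concern holds. As worded, criterion 6 can remove patients after randomisation, and the statistical plan does not keep them in. The same applies to criterion 5 only if it is judged by the fixation actually used. The point does not extend to anaesthetic conversions, which the plan retains as outcomes.

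Size and direction cannot be derived from the documents. The bias is zero if removal is unrelated to outcome, or is equal in both arms with the same prognosis. It is small when exclusions are few or nearly balanced, and material when they fall mainly in one arm. A tilt towards WALANT is plausible if a poor field leads to a change of technique; the opposite is equally possible arithmetically. The conclusion rests on two readings: that allocation precedes surgery, and that criterion 6 describes an operative event. This should be fixed, with medium confidence, because outcomes of patients dropped without follow-up cannot be recovered later.

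**What to change.** - **Section 3.2:** delete criterion 6 as an exclusion, and reword criterion 5 so that eligibility depends on the fixation planned before randomisation. The reworded criterion 5 keeps any intended restriction on technique.
- **Section 3.6:** state that all randomised patients are followed and analysed in their allocated group, whatever fixation, tourniquet use or anaesthetic conversion follows. Keep the subset treated as planned for a sensitivity analysis only.
- **Section 3.3:** add two variables for both arms: the fixation or technique actually used, with the reason for any change; and any tourniquet use (yes/no, minutes). Report both by arm.

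The cost is some wording and two items on the data form, with no extra patients or visits. The drawback is slightly more variety of fixation in the analysed groups. These changes concern eligibility timing, recording and analysis; they prescribe nothing about how patients are operated on or anaesthetised.

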3.3. VARIABLES

Independent variables:

These variables will be collected during the surgery and in the subsequent from patient anamnesis, clinic history and filling the Collection Data Guide Form:

- Age (years)
- Sex (male / female)
- Dominant hand (left / right / both)
- Injured hand (left / right / two)
- Fracture classification according to American Orthopaedic (AO) (16), (17)
- Number of days from injury to surgery (days)
- Preoperative pain (VAS scale (18))
- Preoperative swelling injured hand and healthy hand. The perimeter of the wrist will be measured at the height of the proximal palmar fold in cm.

Dependent variables:

These variables are the ones we want to study and will be collected during the surgery and afterwards from patient anamnesis, clinic history and filling the Collection Data Guide Form:

- Duration of admission (hours).
- Duration of surgery (minutes).
- Duration of ischemia in group B (minutes).

- Preoperative and postoperative pain (VAS scale): Pain at baseline, 24 hours post-intervention, at the visit of the first treatment 10-15 days post-intervention and pain 1 month after the intervention.
- Intraoperative pain (VAS scale): Assessable only if it has not required sedation.
- Time (minutes) of anaesthesia administration
- Time (minutes) from the end of administration to the beginning of IQ
- Need for anaesthetic reinforcement:
 - Sedations (yes/no) and reason
 - In the case of WALANT: Taking into account the reference technique used (10), if any extra doses are needed and location within the wrist
- Postoperative analgesia during admission and discharge (drugs used, dose and frequency of use)
- Postoperative swelling injured hand and healthy hand (cm).
- Stained dressing and the presence of active bleeding due to the wound within 24 hours and during the first outpatient clinic 10 or 15 days after surgery.
- Patient satisfaction during the first outpatient clinic 10 or 15 days after surgery. → Assess satisfaction (1-5) / Would you repeat the anaesthesia type? / Would you recommend the technique?
- Description of the complications of anaesthesia.
- Description of postoperative complications.
- Mobility 24 hours post-intervention, first aid and one month later. (The mobility of the fingers, intrinsic and extrinsic muscles, Kapandji exercises 1-10 and wrist mobility will be assessed by measuring flexion-extension and prone-supination with a goniometer).
- Surgeon's experience
 - a. Technical difficulty due to lack of visualization in the surgical field (Scale 1-5. 1 no difficulties, 5 very difficult))
 - b. Added stress to the surgery (yes/no) and reason.

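### Need for added anaesthesia is a two-arm outcome in 2.2, but 3.3 prompts for extra local doses only under WALANT and files elective sedation as reinforcement

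*Combined protocol and SAP*

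**What the plan says.** Section 2.2, item 4, makes insufficient anaesthesia a secondary outcome. Part 4a is conversion to general anaesthesia. Part 4b is "Need of adding more anaesthesia", followed by "Type of anaesthesia used (sedation, local anaesthesia reinforcement, etc" and a reason. No arm is named anywhere in the item.

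Section 3.3 has a corresponding variable under an arm-neutral heading, "Need for anaesthetic reinforcement", with two sub-items:

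- "Sedations (yes/no) and reason", which applies to both arms;
- "In the case of WALANT: Taking into account the reference technique used (10), if any extra doses are needed and location within the wrist", which applies to group A only.

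Section 3.4 makes sedation elective in both arms: "all patients will be offered the option of sedation or not". The section then says that the choice is not fixed: "this variable may change depending on the criteria of anaesthesia or the patient himself". The same section lets the surgeon raise the WALANT volume within the toxic limit, without saying when. Section 3.5 (limitations) says that block doses will differ between patients according to the anaesthetist. Section 3.6 compares qualitative variables between arms by chi-square or Fisher's exact test at the 5% level.

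**The concern.** A between-arm comparison of an event needs the event to be sought equally in both arms. Here one arm has a specific prompt for a non-sedation top-up and the other has none. A supplementary infiltration or repeat block in group B would then be noted only if someone thought to write it down. Missing events in one arm make the other arm look worse, so the error would run against WALANT. The plan's main objective includes whether the technique is applicable, and adequacy of anaesthesia bears directly on that.

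Sedation raises a second problem within the same variable. If sedation that a patient chose beforehand is counted as reinforcement, the outcome mixes preference with failure of the anaesthetic, and a real difference in either direction is diluted. A reason is recorded, but nothing says which reasons count.

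**Working it through.** **Comparison of the texts**

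| Component of 4b | 2.2 | 3.3, group A | 3.3, group B |
|---|---|---|---|
| Sedation | yes, no arm named | yes/no and reason | yes/no and reason |
| Extra local anaesthetic | yes, no arm named | extra doses and site | no specific item |
| Repeat or supplementary block | covered only by the open-ended list of types | not applicable | no specific item |
| Rule separating elective from rescue sedation | none | none | none |

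The gap between the arms is therefore confined to non-sedation top-ups. Group A has a reference technique against which an extra dose can be judged. Group B has no fixed dose, so a top-up cannot be inferred afterwards from the total given.

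**Illustration of size.** The plan gives no sample size, top-up rate or sedation rate, so there is no figure to reproduce. All inputs below are assumptions.

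- t: true top-up rate, equal in both arms (5%, 10%, 20%)
- s: sedation rate, equal in both arms and independent of top-up (20%, 40%)
- c: share of group B top-ups captured
- n: 40 per arm

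For an endpoint of sedation or top-up (pooling that the plan does not specify):

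- recorded rate in A = 1 − (1 − s)(1 − t)
- recorded rate in B = 1 − (1 − s)(1 − tc)
- false difference = t(1 − s)(1 − c), whatever the sample size

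Example: t = 10%, s = 20%, c = 0 gives A = 1 − 0.8 × 0.9 = 28%, B = 1 − 0.8 = 20%, difference 8 points.

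The chance of p<0.05 comes from exact enumeration of two binomial counts, two-sided, with chi-square if all expected counts exceed 5 and Fisher otherwise (the 3.6 rule). With c = 0:

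| t | s | A vs B | False difference | Chance of p<0.05 |
|---|---|---|---|---|
| 5% | 20% | 24% vs 20% | 4 points | 7.1% |
| 5% | 40% | 43% vs 40% | 3 points | 6.2% |
| 10% | 20% | 28% vs 20% | 8 points | 13.2% |
| 10% | 40% | 46% vs 40% | 6 points | 9.0% |
| 20% | 20% | 36% vs 20% | 16 points | 35.5% |
| 20% | 40% | 52% vs 40% | 12 points | 20.3% |

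With half captured (c = 0.5), the chance is 6.8% or 6.4% at t = 10% and 11.6% or 9.3% at t = 20% (s = 20% or 40%). With full capture it is 4.9% to 5.6%. For 25 to 60 per arm with none captured, the ranges are 5% to 8% at t = 5%, 9% to 18% at t = 10% and 16% to 51% at t = 20%.

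**Top-ups analysed alone.** Fisher's test, 30 or 50 per arm, true rate 10% to 30% in both arms:

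| Group B capture | False difference | Chance of p<0.05, n = 30 | Chance of p<0.05, n = 50 |
|---|---|---|---|
| Half | 5 to 15 points | 1.9% to 19.2% | 6.3% to 35.4% |
| None | 10 to 30 points | 7.3% to 92.3% | 38.4% to 99.9% |

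With equal capture the chance is 0.9% to 3.1% over both sample sizes. Under half or no capture, nearly all rejections point to more reinforcement in WALANT.

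**Dilution by elective sedation.** Assume 40 per arm and true reinforcement of 20% vs 5%. Power is 43.9% if only reinforcement counts. If 20% of patients also have pre-chosen sedation and it is counted, the rates become 36% vs 24% and power 21.1%. At 40% they become 52% vs 43% and power 13.8%. This assumes that the recorded reason is ignored at analysis.

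**The case against.** The strongest reply is that the WALANT line is technique-specific detail. A reference infiltration and a site within the wrist make sense only for group A, just as ischaemia time is listed only for group B. Both the 2.2 outcome and the 3.3 heading are arm-neutral, and the list of types in 2.2 is open-ended, so a repeat block fits. The 3.3 list is also not exhaustive: it omits conversion to general anaesthesia, which is outcome 4a. The data collection form that would settle the matter is not in the text. Section 3.3 also names clinic history as a source, and it has a free-text item on complications of anaesthesia.

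All of this stands against one tempting inference, that group B top-ups will go unrecorded. The documents do not support that. What remains is that neither 3.3 nor 3.4 gives a specific prompt for a non-sedation top-up in group B. The back-up sources are weak: nothing directs anyone to search the history for top-ups, and a successful top-up need not be called a complication.

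On sedation, the reply is that 2.2 speaks of need and sits under insufficient anaesthesia, and that the recorded reason allows the two kinds to be separated at analysis. That is fair, but the rule for doing so is unwritten, and the choice would otherwise be made after the data are seen.

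**Conclusion.** The point holds as a conditional one of minor severity. If collection follows 3.3 as written, non-sedation top-ups in group B risk being under-recorded relative to group A, and this one secondary comparison would tilt against WALANT. Separately, the plan does not say which sedation counts as insufficient anaesthesia.

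The size cannot be estimated from the documents. Under the assumed inputs for the pooled endpoint, the effect on false-positive risk is close to nominal when top-ups are rare (5%) or half are captured at a 10% rate. It becomes large only when top-ups are common and almost none are captured in group B. Analysed alone, top-ups are more sensitive to missing capture, but the same unknown rates govern the result.

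A reader might infer that the trial's main comparison is biased. It is not on this ground: the asymmetry does not touch pain, swelling or satisfaction, nor sedation or general anaesthesia as events. It concerns part of one of five secondary outcomes.

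**What to change.** In 3.3, replace the WALANT-only sub-item with one item recorded at surgery in both arms: any added local anaesthetic, repeat or supplementary block, rescue sedation or general anaesthesia given for pain or inadequate anaesthesia after the end of the initial administration (yes/no, type, dose, time, reason). The time anchor needs little new work, because 3.3 already collects "Time (minutes) from the end of administration to the beginning of IQ".

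Then:

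- keep wrist location and extra dose against the reference technique as descriptive detail for group A;
- record sedation chosen in advance separately in both arms, and do not count it as insufficient anaesthesia;
- state that a larger first infiltration, given before the end of the initial administration, is not an extra dose, since 3.4 does not say when the volume may be raised;
- compare the arms on this single definition with the 3.6 test.

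The cost is a few form fields and one definition, with no extra visit, test or patient and no change of dose. If the form already has a group B field, it is enough to align 3.3 with it and add the sedation rule and the extra-dose definition. One weakness stays: the reason remains a judgement by staff who know the arm. The change belongs at data collection, because a top-up not noted at surgery may not be fully recoverable later.
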